1.18 Indicate any payments or reimbursements to participants (check all that apply)

- Check

1.19 Does this study have a plan to have an individual or committee review combined data from all participants on a periodic basis (such as summary or aggregate safety and/or efficacy data)?

Yes, but it's not described in an attached protocol

Drs. [name] and [name] will have primary responsibility for the monitoring of subjects. Data to be reviewed will be coded with a subject number and will not contain identifiable information. Data will contain summary reporting. This will be shared on an annual basis with the sponsor, or as needed. All incidental findings will be reported to the IRB upon occurrence. All adverse or serious adverse events will be reported to the sponsor and the IRB shared upon occurrence. The investigators and the engaged research team will meet weekly, or as needed, to review accrued data (neuroimaging and behavioral results) and confirm confidentiality of data files.

1.20 What have you done to minimize any risks?

- No foreseeable risks

1.21 What are the potential benefits related to this project for:

- the participant (if any)
- benefits to society (if any)

There are no direct benefits to participants in this study.

This project has high relevance for public health by providing a rigorous and comprehensive evaluation of the effects of mindfulness training on psychological and brain function in healthy young adults. Although mindfulness practices are rapidly gaining in popularity as a lifestyle intervention to enhance psychological health and well-being, the brain basis of their effects are still not well-understood, particularly in healthy populations. The knowledge gained from this project will promote greater understanding and more informed decision-making regarding the potential benefits to be gained from instruction and training in mindfulness.

1.22 Provide a summary of the analysis methods you will use, including, if applicable, the data points or outcomes you will analyze.

Standard statistical analyses using a within subjects factorial ANOVA, t-test or regression. All data points will be included, which include experimental conditions (e.g., delay, target location). Dependent measure will be saccade accuracy.

1.23 Provide the rationale or power analysis to support the number of participants proposed to complete this study.

Estimates of power for all of our primary analyses are over 80% power to detect a medium or even small effect size with the proposed sample size. We are looking for extremely subtle effects in the data, including time-dependent changes in accuracy.

1.25 Will any data from this project be stored for use in future research studies?

Yes - contribution for future use is mandatory for participation in the study

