4.17 Will any external monitors require access to this study in Epic?

No

4.19 Mark all that apply to your study:

1. Protocol

1.1 Is there a separate, written protocol that will be submitted in addition to this form? (Note: a grant application is not considered to be a protocol)

No

1.2 Select up to three key words below that best describe this research study:

- Psychology
- Clinical

1.3 Provide a short summary/abstract of the purpose and procedures of the study proposed in this IRB application.

- DO NOT include information on studies not proposed in this application.
- Use LAY terminology only. This must be easily understandable by IRB community members and nonscientists.
- DO NOT cut and paste technical abstracts from source of support applications that may not be understood by a general audience.

This project focuses on understanding the cognitive and neural mechanisms by which mindfulness training (MT) results in positive behavioral change and enhanced psychological well-being. Building upon research by the Human Connectome project and the Dual Mechanisms of Cognitive Control studies, we will recruit MZ and DZ twins and non twin siblings, to participate in fMRI sessions.

The subjects will be recruited in pairs, with one subject randomly assigned to the MT condition (mindfulness-based stress reduction, or MBSR; the most-validated and standardized form of MT instruction) and the other serving as a (wait-list) control. Each co-subject will undergo extensive behavioral and MRI neuroimaging assessments in a pre/post fashion, before and after the MT (or no-contact control) intervention, to test for specific MT-related effects.

1.4 Specify your research question(s), study aims or hypotheses:

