We will use this design to investigate theoretically-focused hypotheses that stem from our guiding framework regarding the neural mechanisms of cognitive control. Specifically, using a newly developed cognitive control task battery, we will test the counterintuitive hypothesis that MT produces an enhancement in the neural mechanism and circuits associated with reactive (rather than proactive) control. An additional subset of MZ twin participants will undergo retesting with the original HCP protocol, in order to provide a comprehensive assessment and comparison of MT effect sizes across multiple domains of cognitive and brain function. Success in this project will have high relevance for public health, by providing innovative experimental tools and a novel theoretical framework from which to empirically evaluate and better understand the potential impact of MT programs as lifestyle interventions for enhancing psychological well-being in healthy populations.

1.5 Background and significance and/or Preliminary studies related to this project:

Over the last decade, current understanding of the neural basis of complex psychological functions has shifted in emphasis from a focus on specific regions, to that of brain networks, while still highlighting the importance of key nodes within these networks. In terms of attentional and cognitive control, the lateral frontoparietal network(FPN) is generally agreed to be paramount. Within the FPN, dorsolateral prefrontal cortex (dIPFC) regions appear to function as critical hub nodes.

Strikingly, current cognitive neuroscience research has also associated MT with critical changes to each of these networks and key nodes. The FPN, and dIPFC in particular, show MT-related effects that appear to reflect both the state-changes associated with increased focusing of attention during meditative states, as well as potentially trait-related changes due to MT experience that result in more effective utilization of this network during attentional control tasks.

Building upon MZ and DZ research conducted by the HCP and current R37 study on dual mechanisms of cognitive control by [name], we will utilize the tasks and build upon the data of these successful and ongoing studies.

1.6 Literature cited/references (if attaching a grant enter N/A):

N/A

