A. Behavioral Practice Session: Participant will complete 4 behavioral tasks (AXCPT, Stroop, Sternberg and Task-switching) on a computer. Participants will practice the corresponding (counterbalanced order of proactive/reactive) condition of the tasks outside of the scanner before the scanning sessions. These practice sessions will last approximately 30 minutes each. If not completed, subjects will complete any questionnaires remaining from Session I Behavioral Practice.

B. Scanning Sessions:

Participant will perform two scanning sessions in Session II of the study. The sessions will be counterbalanced between the proactive and reactive conditions of the four tasks (AXCPT, Stroop, Task-switching and Sternberg) in a scanner. Scanning will consist of both functional (tasks) and resting state acquisition. Each scan will last approximately two hours. Blood pressure and pulse will be measured prior to the scan.

B: Break

C. Second Scanning Session (of counterbalance)

D. Exit Survey (post-task questionnaire)/Debriefing

One of the twin participants will be randomly selected to participate in an 8-week Mindfulness-based stress reduction (MBSR) program led by certified MBSR instructors at a dedicated facility, supervised by [name]. The MBSR program uses a combination of mindfulness meditation, body awareness, and yoga to help people become more mindful. The MBSR program is an eight-week workshop taught by certified trainers that entails weekly group meetings (two-hour classes) and a one-day retreat (six-hour mindfulness practice) between sessions six and seven, home practice, and instruction in three formal techniques: mindfulness meditation, body awareness, and simple yoga posture.

After the completion of the program, the twins will return for sessions three and four - a repeat/retest of Session I and II.

If participants that have completed or are enrolled in IRB 201510077, Dual Mechanisms of Cognitive Control ([name], PI), they will not complete session one and two. They will be asked to begin at the mindfulness training and complete sessions three and four.

The twin that was not chosen to participate in the MBSR initially will be given the opportunity to voluntarily participate after the completion of the retest sessions.

Task descriptions:

AXCPT:

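### Section 1.22 names a within-subjects analysis without arm, pair or arm-by-time, although arm is randomised between the two members of a pair; taken literally, it does not test the randomised comparison

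*Protocol*

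**What the plan says.** **Analysis (Protocol 1.22).** The method is "Standard statistical analyses using a within subjects factorial ANOVA, t-test or regression". On factors it says "All data points will be included, which include experimental conditions (e.g., delay, target location"), and on outcome "Dependent measure will be saccade accuracy". It mentions no arm, pair, pre/post visit or interaction.

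**Design (Protocol 1.3).** "The subjects will be recruited in pairs, with one subject randomly assigned to the MT condition", with "the other serving as a (wait-list) control". Both members are measured before and after: "Each co-subject will undergo extensive behavioral and MRI neuroimaging assessments in a pre/post fashion".

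**Retest (Protocol 1.13).** After the programme, "the twins will return for sessions three and four - a repeat/retest of Session I and II".

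**Hypothesis (Protocol 1.4).** The claim to be tested is that "MT produces an enhancement in the neural mechanism and circuits associated with reactive (rather than proactive) control".

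**Size (Protocol 2.1.a).** 50 adults are expected, hence at most 25 pairs.

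**The concern.** In section 1.3 a subject is one person, and each person is in one arm only for the comparison. A within-subjects factorial ANOVA in that sense holds only factors that vary inside a person: visit, task, control mode. It can show that people changed, but not that trained members changed more than their wait-list co-subjects, which is the question the randomisation was set up to answer.

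Two things are at stake. First, the retest repeats the same sessions, so improvement through practice is plausible in both arms. The wait-list arm guards against this only if the analysis uses it. Second, section 1.22 also allows a t-test or regression without saying on what unit. If persons are compared and the pairing is ignored, the precision gained from matching is lost.

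The rest of section 1.22 does not help the reader infer the right comparison. Its example factors and its outcome belong to an eye-movement task, and section 1.13 describes none. The section 1.4 hypothesis needs a contrast of arm by time by control mode, and nothing in section 1.22 points to it.

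**Working it through.** **The plan's own figure.** Section 1.22 contains no number. Section 1.23 claims power above 80%, but gives no alpha, numeric effect size, SD or correlation, so it cannot be reproduced from its inputs. It is not used below.

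**Inputs.**
- From the documents: 50 adults (2.1.a), so at most 50/2 = 25 pairs; 1:1 allocation within pair (1.3); the same sessions repeated (1.13).
- Assumed, because the documents give no values: two-sided 5%; no dropout; practice gain g = 0.2 to 0.3 SD of the score, equal in both arms; pre/post correlation r = 0.5 to 0.7; within-pair correlation of change rho = 0.3 or 0.5; where power is computed, a training effect of 0.6 SD of change.

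**Step 1. Pre/post test in the trained arm, with no training effect.** The SD of change is sqrt(2(1-r)) SDs of the score, so the standardised practice change is dz = g / sqrt(2(1-r)). The rejection rate is that of a one-sample t-test with n = 25, 24 df and noncentrality dz x sqrt(25).

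| g | r | dz | noncentrality | rejects |
|---|---|---|---|---|
| 0.2 | 0.5 | 0.200 | 1.00 | 16% |
| 0.2 | 0.7 | 0.258 | 1.29 | 24% |
| 0.3 | 0.5 | 0.300 | 1.50 | 30% |
| 0.3 | 0.7 | 0.387 | 1.94 | 46% |

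A time effect pooled over all 50 persons, treated as independent, rejects in 28% to 77% over the same grid.

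**Step 2. Within-pair comparison of change, same conditions.** An equal practice gain cancels in the difference between co-subjects, so the test keeps its size. In simulation (25 pairs, 20,000 runs per setting, practice gain 0, 0.3 or 0.5 SD of change, rho 0 or 0.5) the paired test rejected in about 5% throughout.

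**Step 3. Comparing persons and ignoring the pair.** In SDs of change:
- Unpaired standard error: sqrt(2/25) = 0.283.
- Paired standard error: sqrt(2(1-rho)/25) = 0.237 at rho = 0.3 and 0.200 at rho = 0.5.
- Ratio 1/sqrt(1-rho): 1.20 and 1.41, so the unpaired standard error is 20% or 41% too wide.
- Actual size of the nominal 5% test, by simulation: about 2% and 0.7%.
- Power at 0.6 SD of change, paired: noncentrality 0.6/0.237 = 2.54 and 0.6/0.200 = 3.00, giving 68% and 82%. Unpaired, by simulation: about 55% and 57%.

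**Step 4. Which mixed model recovers the pairing.** Random intercepts for pair and person are constant over the two visits and cancel out of pre/post change. A model with only these treats co-subjects' changes as independent and keeps the standard error near 0.28 at either correlation. A pair-by-time random effect, or a direct analysis of the pair differences in change, is needed to reach 0.237 or 0.200.

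**The case against.** The strongest reply is that section 1.22 offers three alternatives. A t-test on within-pair differences in change, or a regression with an arm term, would fit the sentence. An ANOVA that takes the pair as its unit can carry arm as a repeated factor. The factor list is introduced as examples only. This stands: a reader might infer that the plan excludes the randomised comparison, or that practice gains will be reported as training effects. The documents support neither. Section 1.3 provides a concurrent control assessed at both visits for the purpose of isolating training effects, and no section plans a test in the trained arm alone.

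It can also be said that section 1.22 is a summary on an ethics form, and that random effects and a designated primary contrast commonly belong in a statistical analysis plan. That stands for the model details. It does not cover the label: the section states a method, and that method in its ordinary person-level sense does not fit the design. To rescue it, one must add terms it does not contain or use the word subject differently from section 1.3.

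Finally, every magnitude above rests on assumptions. That is true. Ignoring the pair also errs on the safe side for false positives when rho is positive; its cost is power.

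**Conclusion.** The point holds conditionally. Section 1.22 names neither arm, pair nor arm-by-time, and its one specific design label, within subjects, does not fit a trial randomised between co-subjects. If the section is followed literally at person level, the randomised contrast goes untested and practice cannot be told from training. The sentence permits a valid paired test, an inefficient unpaired test and a misleading pre/post test alike, so it is badly fixed rather than merely brief.

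On the assumptions listed, the pre/post test in the trained arm would be falsely significant in 16-46% of trials, against 5% for the within-pair comparison. Ignoring the pair would cut power at 0.6 SD of change from 68% to about 55% (rho 0.3), or from 82% to about 57% (rho 0.5). These figures show the scale of the problem if the wrong option is taken; they do not predict what the investigators will do. Because the affected comparison is the purpose of the trial, the text should be settled before analysis.

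**What to change.** Replace the text of section 1.22 with wording to this effect:

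> The primary test is the within-pair difference (trained minus wait-list co-subject) in pre/post change, by a paired test on the pair differences or an equivalent mixed model with arm, time, arm x time and a pair-by-time random effect as well as pair and person effects. The section 1.4 hypothesis is tested by the same within-pair difference applied to the reactive-minus-proactive change (arm x time x control mode). Pre/post change within the trained arm is descriptive only.

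In the same edit, replace the eye-movement outcome and the delay and target-location conditions with an outcome and conditions from the tasks in section 1.13. Changing the first sentence alone would leave an outcome that no described task measures.

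The cost is a rewrite of section 1.22. It needs no new data, visits or participants.

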A. Intake: This will involve a brief interview and data on standard physiologic information (height, weight, blood pressure, and pulse). If blood pressure is considered high, participant will be given an information sheet at the end of their session. All participants will then be administered the MRI screening form and demographic form. If participant is deemed eligible, the experiment will commence. If they are ineligible, they will be told why and will be withdrawn from the study.

B. Behavioral Practice Session (This will take approximately 2 hours.)

1. TASKS: Participant will complete 4 behavioral tasks (AXCPT, Stroop, Sternberg and Taskswitching) on a computer. Subjects will complete the Operational and Symmetry Span tasks, an 18 item Ravens Matrices task, a breath counting task, and a Letter Set task.

2. Questionnaires:

Subjects will also complete behavioral questionnaires during practice sessions, which include: Behavioral Inhibition System/Behavioral Approach System (BIS/BAS)

Need for Cognition Scale (Nfc)

Generalized Reward and Punishment Expectancy Scales (GRAPES)

Mindful Attention Awareness Scale (MAAS)

Five Facet Mindfulness Questionnaire (FFMQ)

Pittsburgh Sleep Quality Index

State Trait Anxiety Inventory (STAI)

Domain Specific Risk Taking(DOSPERT)

The Positive and Negative Affect Schedule(PANAS)

Sensitivity to Reward and Punishment Questionnaire

Self-Scoring Self Control Scale (SSC)

Barratt Impulsiveness Scale (BIS)

Alcohol&Smoking Questionnaire

Neo FFI

Fordyce

Patient health questionnaire (PHQ0

Satisfaction with Life (SWL)

Self Compassion scale (scmp)

Pittsburgh sleep quality index (PSQI)

Exit Satisfaction Survey

pre & post task questionnaires

C. Break

D. Scanning: In the scanner, participants will perform baseline session of the 4 tasks (AXCPT, Stroop, Task-switching and Sternberg) in a scanner. This will take approximately 2 hours. Blood pressure and pulse will be measured prior to scan. Scanning will consist of structural, functional and resting state acquisition.

E. Review of schedule for Scanning Session II.

Session II and Session III (can either be completed on the same day or broken into two sessions A&B&D, A,C,D):

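### Section 1.22 names saccade accuracy as the dependent measure, but no described procedure records eye movements and the measure does not address the 1.4 hypothesis

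*Protocol*

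**What the plan says.** Section 1.22 proposes a within-subjects factorial ANOVA, t-test or regression, says that all data points will be included, and then specifies "experimental conditions (e.g., delay, target location). Dependent measure will be saccade accuracy". It names no other dependent measure.

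Section 1.4 gives the hypothesis: "we will test the counterintuitive hypothesis that MT produces an enhancement in the neural mechanism and circuits associated with reactive (rather than proactive) control".

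Sections 1.3 and 1.13 describe the design and the data:

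- Allocation (1.3): "The subjects will be recruited in pairs, with one subject randomly assigned to the MT condition", with the other member of the pair as wait-list control.
- Timing (1.3): "Each co-subject will undergo extensive behavioral and MRI neuroimaging assessments in a pre/post fashion".
- Session I (1.13): "participants will perform baseline session of the 4 tasks (AXCPT, Stroop, Task-switching and Sternberg) in a scanner". On the scans: "Scanning will consist of structural, functional and resting state acquisition".
- Sessions II and III (1.13): "The sessions will be counterbalanced between the proactive and reactive conditions of the four tasks".

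**The concern.** A saccade is an eye movement, so its accuracy can be scored only if gaze is recorded. Section 1.13 describes a battery answered by hand or voice, with MRI, and mentions no gaze recording. The outcome in 1.22 therefore appears to belong to a different experiment from the one described.

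Two things are at stake. First, an analyst who follows 1.22 literally has nothing to analyse. An analyst who departs from it must choose among four scanned tasks, five further tasks, a long list of questionnaires and several scan types, and the protocol's outcome statement does not constrain that choice before the data are seen. Second, the hypothesis is about a neural mechanism. Even if saccade accuracy were collected, it would be a behavioural measure from outside the battery that 1.4 says will be used.

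**Working it through.** No arithmetic beyond counting applies. The check compares each task, response mode, manipulated factor and scan type in section 1.13 with what 1.22 names, and then compares 1.22 with 1.4.

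**Step 1: can any described task yield saccade accuracy?**

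| Task (1.13) | Response as described | Eye movements recorded? |
|---|---|---|
| AX-CPT (scanned) | Button | Not described |
| Sternberg (scanned) | Button | Not described |
| Stroop (scanned) | Voice, saved as audio | Not described |
| Task-switching (scanned) | Keyboard | Not described |
| Operation Span | Verifying sums, recalling words | Not described |
| Symmetry Span | Arrow keys | Not described |
| Ravens Matrices | Device not stated | Not described |
| Letter Set | Device not stated | Not described |
| Breath counting | Keys | Not described |

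Result: 0 of 9 described tasks are said to record eye movements, and 4 of 4 scanned tasks state a manual or vocal response.

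**Step 2: can the scanning yield it?** Three scan types are described: structural, functional and resting state. Eye tracking is mentioned for 0 of 3. Section 1.16 answers yes to audio, video or photographs, but the only such recording described is the Stroop audio file.

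**Step 3: do the example conditions match?** The factors that 1.13 says are varied across the baseline, proactive and reactive versions are:

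- AX-CPT: the numbers of each trial type.
- Sternberg: list length, load and frequency.
- Stroop: proportion of congruent items.
- Task-switching: intervals and congruency.

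Target location is not among them. The nearest candidates do not fit. AX-CPT target trials are a cue-probe combination, not a position. The Symmetry Span grid positions are items to be remembered, not a stated condition. Delay is different: it could refer to the Sternberg maintenance period or the task-switching intervals, but 1.22 ties it to no task.

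**Step 4: does the outcome address the hypothesis?** Section 1.4 concerns neural circuits of reactive versus proactive control, tested with the cognitive control battery. The relevant data are functional scans during the four tasks in the baseline, proactive and reactive conditions, before and after training, compared between members of a pair. Section 1.13 collects these. Section 1.22 names something else.

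**Step 5: is the term supported elsewhere?** Saccade and target location each appear once in the protocol, both in 1.22. Section 1.19 describes the accruing data as neuroimaging and behavioural results.

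Count: 1 of 1 dependent measures named in 1.22 has no source in the described procedures.

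**The case against.** The strongest reply is that this is one careless sentence in a short summary answer on an IRB form, and that the rest of the document shows what is meant. Section 1.22 itself says all data points will be included, 1.4 ties the hypothesis to the task battery and to a neural mechanism, and 1.23 speaks of primary analyses in the plural. A grant application is listed as attached but is not shown. All of this is fair. The statement that the right data are not named should therefore be confined to 1.22: the protocol contradicts itself rather than being silent throughout. But none of it supplies a source for saccade accuracy. Section 1.22 is where the outcomes are asked for, and section 1.1 says no separate written protocol will be submitted.

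Deferring the matter to a statistical analysis plan does not help. This is not a missing detail but a definite statement that such a plan would have to follow without data or contradict.

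Two limits on scope also stand:

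- Section 1.4 says "An additional subset of MZ twin participants will undergo retesting with the original HCP protocol" and describes none of the procedures. Whether that retest records eye movements cannot be told from the protocol. It covers only a subset and could not provide the single outcome for the whole study.
- Participants who completed or are enrolled in study 201510077 skip sessions one and two, so their pre-training data would have to come from that study, whose procedures are not shown. For them, the description of data collected before and after training under this protocol is too broad. This does not rescue saccade accuracy.

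Finally, it is plausible that the wording was carried over from another study, but the document does not say so and the finding does not depend on it.

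**Conclusion.** The concern holds and must be fixed. The only dependent measure named in 1.22 has no data source in the described procedures (0 of 9 tasks, 0 of 3 scan types), one of its two example conditions matches no described manipulation, and the measure does not test the hypothesis in 1.4. The design is not broken: the data needed for the hypothesis are described in 1.13, subject to the limit on participants from study 201510077.

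The conclusion rests on the procedures as described and makes no claim about the undescribed HCP retest.

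There may be a knock-on effect in section 1.23, which claims over 80% power and refers to changes in accuracy over time without naming a task. If that means saccade accuracy, the power statement also concerns a measure that is not described as collected.

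**What to change.** In section 1.22:

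- Delete saccade accuracy and target location. Keep delay only if it is tied to a named task.
- Name as dependent measures task fMRI activity and the behavioural measures from AX-CPT, Stroop, Sternberg and task-switching. If the investigators also intend questionnaire scores or the HCP measures as outcomes, name those too.
- State the comparisons the design already contains: control condition (baseline, proactive, reactive), pre versus post, and mindfulness training versus wait-list within pairs.
- Identify the reactive-control neural effect as the test of the 1.4 hypothesis. Regions and contrasts can be left to the statistical analysis plan.

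In section 1.23, say which task's accuracy is meant, and correct the clause if it refers to saccades.

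The cost is wording: 1.22, and possibly one clause of 1.23. No new task, scan or participant is needed, because the replacement outcomes come from procedures already described in 1.13. For participants who enter from study 201510077, the text should say that their pre-training measures come from that study.

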2.1 Will there be any adult participants?

Yes

2.1.a How many adult participants do you expect to consent or enroll under a waiver for this project?

50

2.1.b What is the age of the youngest adult participant?

18.0

2.1.c What is the age of the oldest adult participant?

45.0

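### Section 1.23 claims over 80% power for a small effect in every primary analysis, but 50 people in at most 25 randomised pairs give about 16% at a within-pair standardised difference of 0.2

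*Protocol*

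**What the plan says.** The sample-size rationale in Protocol section 1.23 is two sentences long. The first claims, for all primary analyses, "over 80% power to detect a medium or even small effect size with the proposed sample size". The second adds: "We are looking for extremely subtle effects in the data, including time-dependent changes in accuracy". No alpha, sidedness, numerical effect size, standard deviation, correlation or named test is given.

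The other relevant statements are:

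- **Number.** Section 2.1.a asks "How many adult participants do you expect to consent or enroll under a waiver for this project"; the answer is 50.
- **Design.** Section 1.3: "The subjects will be recruited in pairs, with one subject randomly assigned to the MT condition". The co-member is a wait-list control, and both are assessed before and after the training period.
- **Aim.** Section 1.4: "we will test the counterintuitive hypothesis that MT produces an enhancement in the neural mechanism and circuits" of reactive control.
- **Methods.** Section 1.22: "Standard statistical analyses using a within subjects factorial ANOVA, t-test or regression".
- **Outcome.** Section 1.22: "Dependent measure will be saccade accuracy".

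**The concern.** The power claim is universal: it covers every primary analysis and extends to small effects. The aim in section 1.4 concerns what the training does, and the randomised evidence on that is a comparison within at most 25 pairs. Paired samples of that size ordinarily detect differences of rather more than half a standard deviation, not a fifth of one.

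This is the only justification of the sample size in the document, and the sentence after it says that very slight effects are sought, so the stated aim leans on the small-effect half. A reader who accepts the claim could take a null result as evidence that training has no small effect, when the study would probably have missed one.

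**Working it through.** **Inputs from the Protocol.** 50 adults (2.1.a); pairs, one member of each randomised to training (1.3), so at most 50 / 2 = 25 pairs; pre and post measurement (1.3); ANOVA, t-test or regression (1.22); power above 80% (1.23).

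**Assumptions, because the Protocol gives none.** Alpha 0.05, two-sided unless stated; conventional small effects d or dz = 0.2, f = 0.10, f² = 0.02; medium d or dz = 0.5; no dropout, which favours the plan. Here dz is the mean within-pair difference divided by its SD.

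**Reproducing the stated figure.** It cannot be rebuilt from the Protocol, because the inputs are missing. The question is which settings would yield it.

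**1. Paired t-test, 25 pairs.** Power comes from the noncentral t with df = 24 and noncentrality dz·√25. At dz = 0.2 the noncentrality is 0.2 × 5 = 1.0, against a critical value of 2.064.

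| Setting, dz = 0.2 | Power |
|---|---|
| two-sided 0.05 | 16.1% |
| one-sided 0.05 | 25.0% |
| two-sided 0.10 | 25.5% |
| two-sided 0.01 | 5.0% |

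Reaching 80% needs 199 pairs (156 one-sided). The dz detectable with 80% power, two-sided 0.05, is 0.584 with 25 pairs, 0.660 with 20 and 0.749 with 16.

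**2. Other simple contrasts.**

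- Unpaired 25 v 25, d = 0.2: noncentrality 0.2 × √12.5 = 0.707, power 10.7%.
- Regression, one predictor, 50 people: λ = f²·N = 0.02 × 50 = 1.0, power 16.5%.
- Within-person contrast on all 50, dz = 0.2: 28.4% two-sided, 40.1% one-sided.

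**3. Pre/post-by-group ANOVA, ignoring pairing.** λ = N·m·f²/(1 − ρ), with df 1 and 48. With N = 50, m = 2 and f = 0.10, λ = 1/(1 − ρ). Power is 28% at ρ = 0.5 (λ = 2), 43% at 0.7 and 59% at 0.8. Reaching 80% needs ρ of about 0.88.

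**4. Co-twin correlation r needed for 80% at d = 0.2.**

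- d in change-score SD units: dz = d/√(2(1 − r)). Setting dz = 0.584 gives r = 1 − (0.2/0.584)²/2 = 0.94.
- d in baseline SD units, pre/post correlation ρ: dz = d/√(4(1 − ρ)(1 − r)). The r needed is 0.90 at ρ = 0.7, 0.85 at ρ = 0.8 and 0.71 at ρ = 0.9.

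**5. Omnibus group-by-measure interaction.** Same λ as in step 3, df m − 1 and 48(m − 1), f = 0.10, N = 50, sphericity assumed.

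| Measures m | ρ | Power |
|---|---|---|
| 6 | 0.5 | 42% |
| 12 | 0.5 | 61% |
| 24 | 0.5 | 83% |
| 12 | 0.7 | 87% |
| 6 | 0.8 | 86% |

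**6. Medium effect, 25 pairs.** 67.0% at dz = 0.5 two-sided (78.3% one-sided). In baseline SD units with d = 0.5, power is 30% at ρ = 0.3, r = 0 (dz = 0.5/√2.8 = 0.30) and over 99% at ρ = 0.9, r = 0.5 (dz = 0.5/√0.2 = 1.12). The last two are illustrative settings, not bounds.

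**The case against.** The best defence is that section 1.22 lists a within-subjects factorial ANOVA first. Section 1.13 describes four tasks, three control conditions and two occasions, which is 4 × 3 × 2 = 24 cells per person. An omnibus interaction test over 24 measures has 83% power at f = 0.10 and ρ = 0.5, and 98% at ρ = 0.7, and section 1.23 does not limit its primary analyses to a single training contrast. That arithmetic stands. It does not rescue the claim: the test assumes sphericity, ignores the pairing and does not isolate the effect of training, which is the aim in sections 1.3 and 1.4. A claim about all primary analyses also fails if the training contrast falls short.

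A second objection is that 16% depends on reading a small effect as dz = 0.2. That is fair. If d is in baseline SD units, with pre/post correlation 0.9 and co-twin correlation 0.5, dz = 0.2/√0.2 = 0.447 and power is 57%. That is far above 16% but still short of 80%.

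Third, no stated input leads to a wrong result, and the grant application listed in section 2.1 (Source(s) of Support) may contain the calculation. It is not among the documents at hand, so this could not be checked. What can be said is that section 1.23 makes an unqualified claim without the strong conditions it would need.

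**Conclusion.** The concern holds. For the randomised training contrast, the small-effect half of section 1.23 is not delivered by at most 25 pairs without strong assumptions that the section does not state. Across the three listed methods, power for a single training contrast is 16% to 28% under ordinary two-sided 0.05 assumptions (with ρ = 0.5 for the ANOVA). For the paired test the shortfall is about eightfold in pairs: 199 / 25 = 8.0. All figures rest on conventional effect sizes and complete pairs; lost pairs would lower them. The medium-effect half is not refuted: it falls short at dz = 0.5 but is attainable with moderate to high correlation. This must be corrected, because it is the document's only sample-size rationale.

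**What to change.** Change section 1.23 as follows.

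1. Remove the claim for small effects, or state the test, alpha, effect metric and correlations under which it holds.
2. Restate the figure for the planned primary contrast. Possible wording: *Assuming a two-sided 0.05 paired test, at most 25 complete pairs give 80% power for a standardised within-pair difference of about 0.58 (0.66 with 20 pairs, 0.75 with 16).* If another primary test is planned, give its matching figure.
3. State the same inputs behind any medium-effect claim. Removing the small-effect words alone would leave a claim that the paired test does not meet at dz = 0.5 (67%).
4. Bring the sentence on very slight effects into line with the restated detectable difference.
5. Tie the figure to an outcome the study collects. Section 1.22 names saccade accuracy, but the procedures and task descriptions in section 1.13 contain no saccade task.

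The cost is wording only, with no added participants. The stated sensitivity becomes less favourable.
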